## **II. Intermediate Endpoint Assessments**

1. **Heart Rate Variability.** For the 24-hour HRV measurement, patients will be instrumented with a DigiTrak XT Holter ambulatory ECG monitor (Philips Healthcare, Andover, MA). Following instrumentation, patients will be reminded to engage in their normal pattern of activity and to wear the monitor for 24 hours. During that time, if participants experience a high-anxiety event, they will be asked to record the event by pressing an event marker button associated with the monitor. A Laser scanner (DelMar Medical, Irvine, California, USA) will be used to scan the recordings using standard Holter analysis procedures. The labeled beat-to-beat file will then be processed using the DelMar time domain HRV analysis software and the DelMar enhanced 24-hour spectral heart rate variability analysis software. Heart rate variability will be estimated from the standard deviation of all normal R-R intervals (SDNN) and from spectral power summed across each of the following bands: high frequency (0.14 to 0.5 Hz), low frequency (0.05 to 0.139 Hz), very low frequency (0.003 to 0.049 Hz), and ultra-low frequency (0.000015 to 0.0029 Hz). For the purposes of the proposed study, the primary hypotheses will be tested using the SDNN measure of HRV, because it is less affected by artifact and nonstationarities found in the ambulatory environment and is most strongly predictive of increased risk of mortality.[65] Certain medications may affect HRV through effects on the autonomic nervous system. Beta-blockers, for example, are known to increase the tonic levels of several measures of HRV, such as RSA. However, the primary outcome HRV measure, SDNN, is relatively resistant to the effects of beta-blockade.[132] Because sleep apnea may impact HRV, a STOP-BANG sleep apnea questionnaire will be administered.

2. **Baroreflex Sensitivity.** BRS studies will be performed between 0800 and 1000 hours under fasting conditions. In the supine posture, following 5 minutes of quiet rest, 10 minutes of beat-to-beat BP data will be collected using the Finometer PRO Model-1 (Finapres Medical System, Amsterdam, the Netherlands), and 10 minutes of beat-to-beat R-R interval will be collected from an electrocardiogram (ECG) recorded digitally at 1000 Hz. The Finometer instrument utilizes the vascular unloading technique to measure SBP, DBP, and MAP on a beat-to-beat basis, and has been validated against intra-arterial measures under various conditions.[133] Power spectra will be estimated using the Welch algorithm.[134] Power spectra will be derived as the average of 60-second data segments, overlapping by half. BRS will be estimated from the modulus of the cross spectrum of R-R interval and SBP for frequencies ranging from 0.070 - 0.129 Hz. This method produces reliable measures that are comparable to estimates of BRS obtained using the invasive phenylephrine injection technique, widely considered to be the “gold standard” measurement method.[135]

4. Measures of chronic inflammation. Plasma inflammatory biomarkers will be measured by ELISA using commercially available kits. We will examine C-Reactive Protein (hsCRP) using a high-sensitivity assay obtained from American Diagnostica, Inc. (Stamford, CT). We will also measure interleukin-6 (IL-6), an inflammatory cytokine that promotes myocardial hypertrophy and may be elevated prior to increases in CRP levels. On the day of blood work, we will ask participants to hold off taking nonsteroidal anti-inflammatory medications (including aspirin) and antihistamines until after their morning (0700-0800 hours) blood draw.

5. Urinary catecholamines. Patients will be asked to collect urine over a 24-hour period, with samples kept cold by storage in a portable cooler. Samples will be assayed for norepinephrine, epinephrine, creatinine, sodium, and potassium. Catecholamine levels will be expressed as urine concentration ( $\mu\text{g/ml}$ ) per urine concentration of creatinine ( $\text{mg/ml}$ ), yielding norepinephrine and epinephrine values in units of  $\mu\text{g}$  per  $\text{mg}$  creatinine for each sample. This provides catecholamine excretion indices that are corrected for individual differences in body size and urine volume.[142] In prior studies, urinary catecholamine data have proven informative, with low subject burden and excellent compliance.[78, 143, 144] As in these prior studies, excellent compliance with urine collection is achieved by emphasizing to participants the importance of a complete 24-hour collection and by providing detailed instructions on how this can be achieved. The completeness of 24-hour urine collections will be assessed by ascertaining whether 24-hour urinary creatinine excretion falls within boundaries based upon body size, race and gender.[145] Incomplete collections will be repeated.

6. Lipids. Total cholesterol, HDL- and LDL-cholesterol, VLDL-cholesterol, and triglycerides will be assayed from fasting blood samples drawn between 0700 and 0800 hours.

7. Metabolic blood analyses. Other blood components to be analyzed include a metabolic panel, insulin, and HbA1c.

8. Blood biomarker analyses. Participant blood that remains following the aforementioned blood analyses may be banked for potential future analyses examining blood biomarkers, such as proteins or metabolites, related to the interplay of exercise, anxiety, and cardiac disease. Importantly, the ability to bank participants' extra blood is at the discretion of the participants. During the consenting process, participants will be explicitly informed about this optional sub-study, their ability to choose whether or not their blood may be saved, and that their choice does not influence their participation or treatment in the study. Participants will consent by initialing a specific section of the consent form detailing the storage and use of their blood.

### **III. Assessment of Aerobic Capacity**

Graded treadmill exercise testing will be conducted at baseline and at the conclusion of treatment using a protocol developed at Duke and Wake Forest Universities.[146] Subjects will exercise to exhaustion or other standard endpoints (e.g., chest pain, ST-segment depression, etc.) under continuous electrocardiographic monitoring. Expired gases will be analyzed continuously by a Parvo Medics True One measurement system (Parvo Medics, Sandy, Utah). Peak  $\text{VO}_2$  will serve as the primary measure of aerobic capacity.

To obtain a measure of participants' average daily physical activity, participants' will be asked to wear an Actigraph™ activity watch for 7 continuous days. The Actigraph™ GT9X Link features a validated 3-axis accelerometer, and the accompanying software allows for examination of physical activity

[figure not shown]

characteristics and sleep patterns.

#### IV. Assessment of Quality of Life

The proposed interventions may not only reduce anxiety, but also impact a number of other areas of functioning that are considered to reflect “quality of life.” We propose to use a questionnaire battery that includes a measure of general health,[147] resilience,[148] perceived stress,[149] optimism,[150] self-efficacy, and perceived social support.[151, 152] These are clearly exploratory measures and are peripheral to our main hypotheses. However, this information is of interest and can be obtained at minimal additional cost. Further, to obtain a more complete picture of patients’ health, we also will use the Godin Leisure-Time Exercise questionnaire[153] to evaluate exercise habits, the Pittsburgh sleep questionnaire[154] to examine sleep patterns, which may affect anxiety and HRV, the Morisky Medication Adherence Scale[155] and Medication Adherence Behavior Evaluation to identify medication adherence, and a fat-related diet habits questionnaire[156] to examine nutrition habits.

Figure 2

ADD, Anxiety and Depression Detector; PHQ9, Personal Health Questionnaire; HADS-A, Hospital Anxiety and Depression Scale – Anxiety; SCID, Structured Clinical Interview for DSM-5 Disorders; HAM-A, Hamilton Anxiety Rating Scale – Anxiety; ASI, Anxiety Sensitivity Index; GAD-7, General Anxiety Disorder-7 item; STAI, Spielberger State-Trait Anxiety Inventory; HRV, Heart rate variability; BRS, Baroreceptor sensitivity; FMD, Forearm mediated dilation; BP, Blood pressure; BDI-II, Beck Depression Inventory-II; QOL, Quality of Life assessments; Actigraph™, wrist accelerometer; CGI, Clinical Global Impressions Scale.

#### V. Post-treatment Assessments at 3-Months and at 9-Months (Six-month follow-up)

At the conclusion of the 3-month intervention (post-treatment), or at the time a participant may drop out of the study (or in the rare instance of requiring additional or different anxiolytic treatment outside of our protocol), patients will complete the same clinical, biomarker, and psychometric test battery that they completed at baseline. At the 6-month follow-up, we will assess anxiety, patients' exercise habits, any psychiatric treatment, psychopharmacologic medications, aerobic fitness using a 6-minute walk test, and cardiac status, including revascularization procedures and CHD events. This will be a naturalistic follow-up that we have used in previous trials,[157, 158] which will allow us to determine patients' anxiety status 6 months after the conclusion of study-related treatment, along with changes in health habits and measures of quality of life. Figure 2 presents an expanded view of the assessment schedule and design of the study. For clinical events, we carefully will document cardiac-related hospitalizations and

emergency room visits, revascularizations, and any deaths for up to 4 years post-treatment.

Both pre-treatment and post-treatment (3 month) assessments will be performed in the same sequence over 3-4 visits. Following a phone screen, participants will arrive for Visit 1 under normal physiologic conditions (i.e. not fasted and having taken all medications) for an orientation and consenting process. If participants consent to the study, then they will perform the battery of anxiety and quality of life assessments and the physical. For Visit 2, participants will arrive fasted and bring in their medication(s). Blood will be taken followed by HRV and BRS measurements and Holter monitor set-up. After these fasted-required procedures are performed, we will provide food for the participants so they can take their medicine. Then, the Actigraph will be initialized and put on participants' wrists, and they will be given a urine cup to take home. For Visit 3, participants will arrive under normal physiologic conditions except for taking aspirin, NSAIDs, or other medication that will impact vascular dynamics. Participants will return the Holter monitor, Actigraph, and urine cup. Lab procedures will include tests for vascular endothelial function, consisting of forearm-mediated dilation, and aerobic capacity, consisting of the exercise treadmill test. Based on the participants' schedules and time limitations, they may choose to combine Visit 2 and Visit 3. On Visit 4, participants will arrive under normal physiologic conditions. Participants will be randomized. If randomization is to a pill group, participants will immediately visit [name]. If randomization is to exercise training, participants will immediately meet with a staff exercise physiologist to discuss exercise prescription and exercise site location.

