**4. Design & Procedures:** This study will be a single-site, randomized clinical trial of exercise training and anxiolytic medication in the treatment of anxiety in anxious CHD patients without MDD as a primary diagnosis. One hundred fifty men and women aged  $\geq 40$  years with stable CHD and elevated anxiety symptoms (HADS-A scores  $\geq 11$ ) will be randomly assigned to Exercise Training, Medication (escitalopram), or Placebo. Patients will be evaluated for anxiety at baseline, after 3 months of treatment, and at 6-month and annual follow-ups. Three months is ample time to observe cardiovascular conditioning effects, even among older cardiac patients, whose responses are often quite variable, and is also adequate to assess the efficacy of pharmacologic treatment. Comprehensive assessments will include clinical evaluations of anxiety and measures of intermediate surrogate endpoints, including autonomic, vascular, and blood markers of risk. Following the completion of the 3-month treatment program, subjects will undergo a post-intervention repeat assessment. Patients will then undergo a 6-month follow-up evaluation for anxiety and CHD risk status and will be followed annually for anxiety and

Figure 1

clinical events (see [Figure 1](#)). All assessors will be blinded to patients' treatment group assignment; groups receiving a pill will be double-blind. Following completion of the intervention, participants will be advised to contact their referring physicians, if necessary, for further treatment, or they will be referred to appropriate mental health care providers.

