## **12. Data Management and Statistical Considerations**

**Data Analytic Approach.** The basic analytic strategy is a linear model carried out in the MPlus modeling software,[164] with treatment group contrasts as factors, and ethnicity, age, gender, and pre-treatment measure of the outcome variable as the adjustment covariables. The intent-to-treat principle (ITT) will be followed in all models, using full information maximum likelihood available in MPlus to manage missing data. For the case of the primary outcome, HADS-A, the model will include post-treatment HADS-A score as the response, with the predictors including two planned contrast variables representing 1) the two active treatments (exercise and escitalopram) vs. placebo and 2) exercise vs. escitalopram, with ethnicity, gender, age, and pre-treatment level of the HADS-A as the adjustment covariables. The contrast tests among treatment groups will be examined directly, i.e., no omnibus or “gateway” test will be required before interpreting them. In support of the HADS-A outcome, we also will compare the pattern of weekly changes in the STAI scores over time using a repeated measures model with Proc Mixed in SAS (SAS Institute, Cary, NC). The primary biomarker outcome, HRV, will be evaluated similarly. It is possible that a small number of participants may require off-protocol psychotropic medication during the course of the trial. These participants will be included in the ITT analysis and will not be replaced. We also will perform a sensitivity analysis with change in medication included as an adjustment variable in the statistical model. Finally, we will compare the treatments on the number of clinical events using a generalized linear model with the appropriate distributional form (e.g., negative binomial), using the same contrasts and covariates as in the linear model described above.

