In addition to treatment effects, we also will test the hypothesis that pre- to post-treatment change in HADS-A scores will mediate the improvements in intermediate CHD biomarkers. M-Plus allows a direct, formal test of this hypothesis via path analysis modeling. For example, a model will be specified so that both active treatment groups will be contrasted against the placebo arm, with a variable representing the change in anxiety intervening between the treatment contrast variables and post-treatment HRV (with the covariates, pre-treatment HRV, age, ethnicity, and gender). Mediation is tested by examining the product of the two component path coefficients (treatment → mediator → outcome) and its standard error, which yields the point estimate of the mediated effect along with the statistical significance of treatment on post-treatment biomarker (e.g., HRV) via change in HADS-A.[165] We also will explore possible treatment-specific mediators (e.g., change in VO2 mediating change in HRV for the Exercise group). In addition to the above tests, we will examine the impact of dropout on the estimates

of treatment effects using mixture modeling available in MPlus. Specifically, we will examine the primary outcomes using Rubin's Complier-Average Causal Effect Estimation (CACE) model,[166] which estimates the effect of treatment for all participants who adhere to the protocol irrespective of treatment group assignment. We will explore possible moderators of the treatment effect using interaction terms. Specifically, we will examine the possible moderating effects of gender, race, patient expectations, and initial severity of anxiety (e.g., DSM-5 diagnosis for an anxiety disorder); if sufficient numbers, we also plan to explore individual diagnoses by adding treatment interaction terms for these variables simultaneously with the primary model, and using a pooled test of the terms to determine whether the individual terms should be interpreted. Participants who voluntarily drop out of treatment or who are unable to complete our protocol will not be replaced but will undergo follow-up assessment.

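### No HADS-A at week 12 is required after early exit, and the plan does not say whether an exit score is the primary response or is missing

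*Combined protocol and SAP*

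**What the plan says.** Section 4 (Design & Procedures) sets out the general schedule: "Patients will be evaluated for anxiety at baseline, after 3 months of treatment, and at 6-month and annual follow-ups". Part V of that section then gives the post-treatment battery at the end of the 3-month intervention, "or at the time a participant may drop out of the study (or in the rare instance of requiring additional or different anxiolytic treatment" outside the protocol. These occasions are joined by the word or. Part V does not ask for a second battery at 3 months from a patient who has already had the exit battery.

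Section 12 (Data Analytic Approach) says of the primary analysis that "the model will include post-treatment HADS-A score as the response". The analysis is labelled intent-to-treat, "using full information maximum likelihood available in MPlus to manage missing data". Of patients who need off-protocol psychotropic medication it says: "These participants will be included in the ITT analysis and will not be replaced". Later it adds: "Participants who voluntarily drop out of treatment or who are unable to complete our protocol will not be replaced but will undergo follow-up assessment". That follow-up assessment has no stated time. Nothing in the section gives a visit window for the post-treatment score or a rule for exit scores.

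Three other statements bear on this. Section 13 provides for withdrawal of subjects whose symptoms worsen. Section 10 expects fewer than 10% of patients to leave because of drug side effects. The weekly instrument (Section 4 part I, Sections 9 and 13) is the STAI-State, so the weekly contacts do not yield a HADS-A that could fill the gap.

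**The concern.** An exit score and a week-12 score do not measure the same thing. Section 4 justifies three months as the time needed for conditioning and for judging the drug, and Section 9 has dose titration running to week 4. A score taken in, say, week 3 therefore precedes much of the exposure, and not to the same degree in each arm. Exit is also related to the outcome, since worsening symptoms lead to withdrawal and a need for other anxiolytic treatment triggers the battery.

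The plan can be followed in two ways, and each has a cost:

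- **Exit scores used as the response.** The primary variable mixes early, partly symptom-triggered values with week-12 values. Full information maximum likelihood gives no protection, because the value counts as observed. For a patient starting off-protocol treatment, the score largely predates any effect of that treatment. The planned sensitivity analysis would then adjust for a change that had not yet acted.
- **Exit scores treated as missing.** Week-12 data are lost for reasons tied to symptoms during treatment. The likelihood method then rests on missingness being explained by what the model contains. Section 12 lists treatment contrasts, ethnicity, gender, age and baseline HADS-A, but no measure of symptoms during treatment.

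Leaving this open for the primary endpoint also lets the choice be made after the data have been seen.

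**Working it through.** **Inputs from the plan.** Allocation 60:60:30 (Section 9), so 120 active against 30 placebo. From the Power Analysis in Section 12: target contrast 0.45 SD, R-squared 0.20, alpha 0.05 (sidedness not stated; two-sided assumed), attrition 15%, 127 of 150 left after attrition.

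**Assumed, because the documents give no figure.** The timing of exits, the fraction f of the treatment effect present at exit, the split of exits between arms, and how much worse exit scores are.

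**Formula.** Power = Φ(δ/SE − 1.96), with SE = √(1 − 0.20) × √(1/n_placebo + 1/n_active).

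**Step 1: the plan's own figure.** After 15% attrition at the stated allocation, n is 25.5 against 102. SE = 0.8944 × √(1/25.5 + 1/102) = 0.198, and power for 0.45 SD is 0.623. The stated 0.80 is not reproduced. With 127 patients and a two-sided test, an equal split (63.5 against 63.5) comes to 0.81. That is a separate matter. It is noted here because the figures below start from the 4:1 split.

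**Step 2: exit scores used, same exit rate in every arm.** All 150 contribute, so SE = 0.8944 × √(1/30 + 1/120) = 0.8944 × 0.2041 = 0.1826. The expected contrast is 0.45 × [1 − q(1 − f)], where q is the share exiting. With q = 0.15:

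| f | Contrast (SD) | Power |
|---|---|---|
| 1 | 0.450 | 0.693 |
| 0.75 | 0.433 | 0.660 |
| 0.5 | 0.416 | 0.625 |
| 0 | 0.383 | 0.554 |

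The largest loss is 0.15 × 0.45 = 0.0675 SD. Over q from 5% to 25% and f from 0 to 0.75, the contrast runs from 0.34 to 0.44 SD and power from 0.46 to 0.68.

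**Step 3: exit scores treated as missing.** This is the case in Step 1: power 0.623 if the contrast remains 0.45 SD. That is almost the same as f = 0.5 in Step 2.

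**Step 4: the week-12 comparator.** The 0.693 assumes that patients who stopped treatment still show the full effect at week 12. If those 15% keep half of it, the Step 2 formula gives 0.416 SD and 0.625. If they keep none, it gives 0.383 SD and 0.554.

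**Step 5: unequal exit, active against placebo.** Suppose an exit score is h SD worse than the same patient's week-12 score would have been. The bias in apparent benefit is h × (q_placebo − q_active). With 25% exit on placebo and 12.5% on active, overall exit is (7.5 + 15)/150 = 15%, and:

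- h = 0.25: bias 0.25 × 0.125 = 0.031 SD, two-sided type I error 0.053
- h = 0.5: bias 0.0625 SD, type I error 0.064
- h = 1: bias 0.125 SD, type I error 0.105

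With 5% on placebo and 17.5% on active (again 15% overall), the biases have the same size and the opposite sign. With equal rates and equal shifts this component is zero.

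**Step 6: unequal exit, exercise against escitalopram.** Assume no true difference, 20% exit on escitalopram and 10% on exercise, mean exit at week 5, and improvement accruing linearly over 12 weeks. The bias is (0.20 − 0.10) × (7/12) × common improvement. That is 0.03 SD for an improvement of 0.5 SD and 0.06 SD for 1.0 SD, against a planned detectable difference of 0.50 SD.

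**The case against.** A reader might infer that the plan carries the exit score forward as the week-12 value, so that the primary contrast is bound to be diluted. The documents do not support that. In part V the post-treatment label attaches to the end of the 3-month intervention, and a later paragraph of the same part again ties post-treatment to 3 months. The likelihood method for missing data, and the reduction from 150 to 127 in the power calculation, both fit dropouts having no post-treatment score. Mixing is one natural reading of part V, but it is not a stated rule.

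Nor can it be said that later assessment is ruled out. Section 12 promises a follow-up assessment without a time, and the detailed schedule is in Figure 2, which is not available in the text reviewed. Part V speaks of leaving the study, where an exit battery may be all that can be obtained, while Section 12 speaks of leaving treatment.

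The plan also calls off-protocol treatment rare, and it includes a medication-change sensitivity analysis and a complier-average analysis of dropout. Step 4 shows that a week-12 score need not give more power.

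These objections stand, and they limit the claim to an open choice with uncertain consequences. They do not close the gap: neither supplementary analysis deals with time of assessment, and no available text tells staff to obtain the week-12 score.

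A reader might also infer that the 6-month follow-up falls early for dropouts, because the text counts from the end of study treatment. The heading of part V already places it at 9 months, so this is a matter of wording.

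**Conclusion.** The point holds as a gap in what is collected and in how the primary response is defined. It is not shown to be an error in the estimate. Followed as written, the plan either mixes exit scores with week-12 scores or loses the week-12 value in an analysis called intent-to-treat, and it does not say which.

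The size and sign of the consequence cannot be fixed from the documents. If 15% exit equally across arms and exit scores are used, the loss is at most 15% of the effect. Moderate imbalance in exit could move a contrast by a few hundredths of an SD in either direction. A shift above 0.1 SD needs both a marked imbalance and exit scores about a full SD worse. All of this rests on assumed exit patterns.

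The gain from the change is a single defined time point and less scope for bias, with no guaranteed rise in power. Should-fix, moderate confidence.

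**What to change.** - **Section 4, part V.** Keep the exit battery, but as an addition. Obtain the HADS-A at week 12 from randomisation, within a stated window, from every randomised patient who has not withdrawn consent. Include those who stopped or switched treatment, and use telephone or e-questionnaire if they will not attend. Distinguish stopping treatment from withdrawing from the study.
- **Section 12.** Define the primary response as that week-12 score regardless of stopping or switching. State that exit scores serve only as auxiliary data or in a sensitivity analysis.
- **Wording.** Align the description of the 6-month follow-up in part V with its own 9-month heading.

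The change concerns measurement only and leaves treatment and withdrawal decisions as they are. It costs protocol and analysis-plan wording plus about 20 to 25 extra questionnaires (15% of 150 is 22.5), using telephone contacts and an electronic questionnaire platform that the study already has. The downside is that some week-12 scores will be collected in a different mode, and some exited patients will decline. A week-12 score that is not collected cannot be recovered later.
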